11.0 Local Recruitment Methods

11.1 Recruitment Process:

Subjects will be recruited from the clinical practices of U01 site investigators, which in the US is comprised of sites of the Clinical Research Consortium for Studies of Cerebellar Ataxias (CRC-SCA), under central IRB for the U01 study. Patients will also be recruited to the U01 study by notices in ataxia newsletters, e.g. the NAF newsletter, and through flyers. In addition, patients who have previously participated in our ataxia study may be contacted by our study coordinator, as stated in the consent form they signed when they participated in our earlier ataxia studies (under protocol # 0502M67488). Control participants will be recruited through the CMRR volunteer mailing list or in person.

A phone screening interview will be conducted by the study coordinator for MR safety and other inclusion/exclusion criteria using the CMRR safety

screening form. A phone script for this purpose is attached in Supporting Documents.

11.2 Identification of Potential Participants:

Subjects will be identified from among the enrollees of the multi-site U01 clinical study (performed under a central IRB and *not* covered under the current IRB protocol), screened clinically by the lead site of the U01 grant (Houston Methodist Research Institute) for disease stage and referred to UMN for MR safety screening prior to enrollment.

In addition, the research team will utilize the CMRR Center's volunteer pool for recruitment of healthy research volunteers in this protocol. The CMRR Center's volunteer pool is IRB approved under the CMRR Center Grant (HSC# 1406M51205) and information regarding volunteers is publicly available on the CMRR website ([CMRR Policies / Procedures](#)). The control group will also likely include spouses and friends of patient participants who find out about the study through their relation with the patient.

11.3 Recruitment Materials:

Recruitment will be done by the multi-site U01 clinical study under a central IRB. In addition, healthy volunteers will be recruited through the CMRR Center's volunteer pool (IRB approved under the CMRR Center Grant, HSC# 1406M51205).

11.4 Payment:

Subjects will not be responsible for the cost of any study procedure. They will be compensated \$50 for each MRI scan visit. If they need to stop any testing for any reason, they will receive partial payment for their time.

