The sample size calculation for this study is based on imaging data that will be acquired at 6 imaging sites, for a total sample size of 100 subjects, namely a 30 (20 premanifest and 10 early-phase) subjects with the SCA1 mutation, 40 (27 premanifest and 13 early-phase) subjects with the SCA3 mutation and 30 controls. The at-risk subject study by the EASG group, which included imaging data from 26 SCA1 mutation carriers and 9 SCA3 mutation carriers, reported significant VBM alterations in SCA1 and trends in SCA3 (18). Based on these data, a Wilcoxon rank sum test will have 95% power to show a difference between controls (mean = 0.018, SD = 0.019) and SCA (mean = 0.016, SD = 0.0019) with 30 subjects per group ($\alpha = 0.025$ to take into account the two comparisons of SCA1 and SCA3 versus controls, two-tailed test). Note that this power computation is conservative since the EASG study included only at-risk subjects, whereas the current study will include both premanifest and early manifest patients. In addition, based on our MRS preliminary data described above, a Wilcoxon-Mann-Whitney test will have 94% power to show a difference in NAA at baseline between premanifest subjects who have disease onset within the 5 years of the U01 (conservatively estimated at 1/3 of the patients i.e. $n=7$, mean = 1.2) and those patients who remain in the premanifest stage ($n=14$, mean = 2) for the SCA1 group (standard deviation of 0.4, $\alpha = 0.05$, two-tailed test). We will recruit a larger sample size for the SCA3 cohort because: 1) imaging alterations did not reach significance for SCA3 mutation carriers in the at-risk EASG study; 2) the diffusion MRI abnormalities in our preliminary data (see section 2.2) were less pronounced in SCA3 than those in SCA1; and 3) SCA3 is the most common SCA, enabling recruitment of a larger cohort.

15.3 Statistical Analysis:

To compare the imaging biomarkers between SCA1, SCA3 and control cohorts, globally and in a pairwise fashion, we will use Wilcoxon rank sum test. In addition, premanifest carriers and early-stage patients will be compared using Wilcoxon rank sum test. Within each SCA group, premanifest and manifest patients will be compared regarding the biomarkers at baseline and during follow-up. If this approach is not conclusive, cluster approaches will be carried out. Sex will be considered as a biological variable to assess potential sex-based differences in imaging results.

15.4 Data Integrity:

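### Section 15.3 specifies unadjusted Wilcoxon tests for non-randomised groups pooled over 6 imaging sites, so differences in age or site mix could be read as disease effects

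*Protocol*

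**What the plan says.** Section 15.3 fixes the test for both sets of comparisons. For the cohorts: "To compare the imaging biomarkers between SCA1, SCA3 and control cohorts, globally and in a pairwise fashion, we will use Wilcoxon rank sum test". For stage: "premanifest carriers and early-stage patients will be compared using Wilcoxon rank sum test". The one subject factor mentioned is sex: "Sex will be considered as a biological variable to assess potential sex-based differences in imaging results". The stated purpose is to look for sex differences, not to adjust the group comparison.

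Section 15.2 describes "imaging data that will be acquired at 6 imaging sites, for a total sample size of 100 subjects", made up of "30 (20 premanifest and 10 early-phase) subjects with the SCA1 mutation" and "40 (27 premanifest and 13 early-phase) subjects with the SCA3 mutation and 30 controls". Its power figures use the same unadjusted test.

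On controls, section 11.1 says "Control participants will be recruited through the CMRR volunteer mailing list or in person", and section 11.2 adds spouses and friends of patients. Section 8.1 sets a minimum age of 18 and no maximum. Section 5.1 enriches the carrier cohorts for an estimated onset within 10 years; sections 2.1 and 2.2 say that this estimate uses CAG repeat size and current age.

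On scanners, section 15.4 plans phantom-based quality assurance, performance metrics for each site before accrual, and uniform quality control of the data.

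**The concern.** The groups are observed, not assigned, so a valid comparison needs age and site either balanced by design or handled in the analysis. Section 15.3 does neither. A rank sum test takes no covariates, and an analysis plan that follows it literally could not add them.

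Age is the first problem. Carriers are invited partly on an onset estimate that contains current age, while controls have only a lower age limit. Within carriers, stage is linked to age through the same onset model. Site is the second. Quality assurance reduces scanner offsets, but it does not remove a constant offset between sites that all pass, and it does nothing about age. Section 2.1 itself says that the combined imaging protocol has not been validated in a multi-site trial setting.

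The primary goal is to validate these markers. A marker that separates groups because of age or scanner would be wrongly credited with tracking disease.

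**Working it through.** **Inputs from the protocol.** SCA1 30 (20 premanifest, 10 early), SCA3 40 (27 and 13), controls 30, 6 sites; two-tailed α = 0.025 for each SCA-versus-control comparison (section 15.2). Section 15.3 gives no α for the stage comparison; 0.05 is assumed here.

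**Inputs that are assumptions.** The documents give no age gap, age–marker correlation or scanner offset, so ranges are used.

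**The plan's own figure.** Section 15.2 states 95% power for this Wilcoxon test at 30 per group. With the printed control SD of 0.019, simulation gives about 8%. With 0.0019 for both groups, d = (0.018 − 0.016)/0.0019 = 1.05 and simulation gives 94.5–94.8%, which agrees with the stated figure. The printed SD is a separate matter and is no evidence for this point. The reproduction shows only that the design was sized on the unadjusted test.

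**Step 1: pure spurious shift.** No disease effect; the groups differ by δ within-group SDs for another reason. Wilcoxon rejection rate, 20,000 replicates:

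| δ | 30 v 30, α 0.025 | 30 v 40, α 0.025 | 20 v 10, α 0.05 | 27 v 13, α 0.05 |
|---|---|---|---|---|
| 0 | 2.2% | 2.4% | 4.4% | 5.0% |
| 0.2 | 6.4% | 7.2% | 6.8% | 8.5% |
| 0.3 | 12.0% | 14.6% | 10.2% | 13.3% |
| 0.5 | 33.5% | 39.0% | 21.7% | 29.3% |

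**Step 2: age as the mechanism.** Marker = −r × age + √(1 − r²) × noise, with mean ages g SD apart. The spurious shift is then δ = r × g. With 3,000 replicates:

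| r | g | δ | 30 v 30 unadjusted | 30 v 30 age-adjusted ranks | 20 v 10 unadjusted | 20 v 10 adjusted |
|---|---|---|---|---|---|---|
| 0.2 | 0.5 | 0.10 | 4.0% | 2.9% | 5.5% | 5.2% |
| 0.3 | 0.5 | 0.15 | 4.7% | 2.4% | 5.5% | 5.1% |
| 0.5 | 0.5 | 0.25 | 8.8% | 2.2% | 9.5% | 5.4% |
| 0.2 | 1.0 | 0.20 | 5.4% | 2.5% | 6.6% | 4.6% |
| 0.3 | 1.0 | 0.30 | 12.6% | 3.1% | 11.3% | 5.8% |
| 0.5 | 1.0 | 0.50 | 33.7% | 2.9% | 21.2% | 5.1% |

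Small rates are noisy at 3,000 replicates. Repeating the unadjusted 30 v 30 test with 100,000 replicates gives 3.3%, 4.5% and 8.9% for g = 0.5, and 6.3%, 12.5% and 34.2% for g = 1. The ranges 3–9% and 5–34% cover both runs.

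**Step 3: site as the mechanism.** Each of 6 sites has an offset drawn from a normal distribution, its SD given as a fraction of the within-site SD. The 30 SCA subjects are spread evenly. α = 0.025, 3,000 replicates; unadjusted rate, then van Elteren in brackets:

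| Offset SD | Controls spread evenly | Half of controls at one site | 80% of controls at two sites |
|---|---|---|---|
| 0.25 | 2.5% (2.5%) | 2.8% (1.8%) | 3.4% (2.5%) |
| 0.5 | 2.3% (2.5%) | 4.5% (1.6%) | 5.7% (2.2%) |
| 1.0 | 2.3% (2.7%) | 10.2% (2.6%) | 13.0% (3.0%) |

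The inflation comes from imbalance, not from pooling as such.

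**The case against.** The strongest reply has four parts.

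- **A covariate list often belongs in the analysis plan, which is not shown.** This holds for detail. But section 15.3 does not defer the choice: it names a test that cannot take covariates.
- **This is a local protocol for up to 30 participants.** Its recruitment text covers one site, and a matching rule may exist in documents of the wider study. This stands. A reader might infer that the controls are unmatched; the protocol is only silent on matching, so that is not supported.
- **Not every group analysis is a Wilcoxon test, and multi-site work is cited.** Section 15.1 plans tract-based statistics, seed-based connectivity and dual regression, and refers volumetric, voxel-based and spectroscopy analysis to published methods whose covariates cannot be checked here. Section 2.3 cites multi-site volumetric studies as well as pooled spectroscopy. So the point is limited to the comparisons in section 15.3, and it would be wrong to say that pooling is supported for spectroscopy only. Earlier multi-site use does not show that offsets are absent.
- **Bias needs actual imbalance.** Stage is defined by SARA, not age; onset age varies widely at the same repeat length; and enrichment for near onset may narrow any age gap between stages. This stands too. It makes the size unknown, but does not remove the link between age and stage.

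A reader might also infer that adjustment must gain efficiency by 1/(1 − R²), that is 1.11–1.43 for an assumed R² of 0.1–0.3. That needs covariates unrelated to group. With equal groups and a 1 SD age gap, the group–age R² is 0.25/1.25 = 0.20, so the factor is 0.8/(1 − R²): 0.8/0.9 = 0.89 to 0.8/0.7 = 1.14. No general gain in effective sample size can be claimed.

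**Conclusion.** The point holds in limited form. For the cohort and stage comparisons, section 15.3 names a method that leaves age and site uncontrolled, and this protocol states no design feature that balances them. Differences in age or site mix could therefore be read as disease effects; the documents do not show that they will be.

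With no disease effect, the nominal 2.5% rate for 30 versus 30 becomes about 3–9% with a 0.5 SD age gap and 5–34% with a 1 SD gap (r 0.2–0.5), and 3–13% with the uneven site mixes tried. The upper end needs both a full 1 SD gap and r = 0.5. With sites balanced there is no site inflation. Age-adjusted or site-stratified tests stay at about 1.6–3.1%. All these sizes rest on assumed gaps, correlations and offsets; the direction of the risk, given imbalance, does not.

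**What to change.** **Main analysis.** In section 15.3, make the main analysis of each marker one regression (linear, robust or rank-based) over all 100 subjects on group and stage, age, sex and site, with head size for volumes not already normalised. Take the stage contrasts from this same model. If site cells are sparse, use a random site effect or harmonise the data across sites first. Keep the Wilcoxon test, or van Elteren stratified by site, as sensitivity analysis.

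**Recruitment.** At the local site, recruit controls to an age and sex mix similar to the carriers where feasible. This is the only time-critical part, since it cannot be repaired after enrolment.

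**Cost.** Wording and one recruitment instruction; site is known, and section 18.1 already provides for collecting demographic data. Age, sex and 6 fixed sites use 1 + 1 + 5 = 7 degrees of freedom. With five group-by-stage cells, the joint model keeps 100 − 5 − 7 = 88. Fitted to SCA1 alone it would keep 30 − 2 − 7 = 21, with 10 early-phase subjects over 6 sites, or under two per site; hence the joint model. The joint model assumes that age, sex and site effects are common to the groups. Precision falls somewhat if age is strongly imbalanced. In carriers, age also tracks nearness to onset, so the adjusted and unadjusted stage contrasts should be reported side by side.

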16.0 Confidentiality

16.1 Data Security:

Participants will be assigned a unique subject code (determined by the U01 clinical study) and this subject code will be used for all procedures and data collection.

All identifying data and PHI will be kept in the UofM Box Secure Storage. Videotaped SARA exams will be kept at Box.com. Face recognizable video containing PHI will be restricted to local research site (University of MN), HMRICC and central raters of the U01 study. Paper records will be kept in locked file cabinets in the study coordinator's office. Any information included in publications will not include identifying information. If health information is released to an outside institution, it will be in the form of a limited dataset that does not include participant identifiers. A copy of the consent form or other research study information will *not* be placed in the participants' medical, employment, or educational records.

A Certificate of Confidentiality (CoC) was issued automatically for this research; effective October 1, 2017 CoCs are issued automatically for any NIH-funded project using identifiable, sensitive information that was on-going on/after December 13, 2016. The CoC was issued as a term and condition of the U01 award and there will be no physical certificate issued.

17.0 Provisions to Monitor the Data to Ensure the Safety of Participants

17.1 Data Integrity Monitoring.

The PI will supervise the progress of the study, and ensure that data are collected and reported in accordance to protocol. Study progress will be reviewed monthly, as well as on as-needed basis. The PI will utilize reports provided by the study coordinator to ensure continuing enrollment and data summaries provided by the study team members responsible for MRI and MRS data acquisitions.

For independent monitoring, we will utilize the Clinical Monitoring Service of the Clinical and Translational Science Institute (CTSI). The service is provided every 6 months and includes a review of the case report forms, medical records, and regulatory documents by the CTSI Clinical Research Monitor. A summary report that details the study progress, regulatory and subject records that were monitored, and any findings identified during the visit is provided to the PI. Upon addressing any findings, the PI will submit the report together with a description of how the findings were addressed to IRB within 5 days of receipt of the report.

17.2 Data Safety Monitoring

The research team will utilize the CMRR Center's Subject Information Form and adhere to the SOP during enrollment of all research participants in this protocol. The CMRR Center's Subject Information Form and SOP are IRB approved under the CMRR Center Grant (HSC# 1406M51205) and information regarding these procedures is publicly available on the CMRR website ([CMRR Policies / Procedures](#)).

This is not a clinical trial, therefore a data and safety monitoring board is not required. The PI will review each study with the study staff on a monthly basis to determine if unexpected adverse events have occurred. Serious adverse events will be reported as soon as they occur to the IRB. All adverse events will be reported annually to the IRB.

18.0 Provisions to Protect the Privacy Interests of Participants

18.1 Protecting Privacy:

Participants will interact with limited study staff. Demographic information, personal health information and clinical assessments will be obtained by the study physician and/or coordinator, ensuring one or two investigators will be interacting with participants most of the time. Other than the study physician and research coordinator, other staff on this protocol will interact with the subjects only to the extent necessary for MR scans. The consenting process and clinical assessments will take place in a private room with only the study staff, the subject and their caretaker if they desire. We will explain to the subject that they can stop participation at any time if they do not wish to interact or provide requested information. The subject will be told why information is necessary. They can refuse to answer any questions that make them feel uncomfortable. They may take a break, discontinue the testing, or withdraw from the study at any time.

18.2 Access to Participants:

The research team needs to access private information about the participants, such as ataxia diagnosis, disease duration and triplet repeat length in the affected ataxia gene, to be able to evaluate clinical correlates of the MR measures under investigation. In addition, members of the MR professionals committee may need to see information on implants and devices to consult on MR safety and the administrative staff will need to see name and address information to be able to process remuneration.

19.0 Compensation for Research-Related Injury

19.1 Compensation for Research-Related Injury:

In the event that this research activity results in an injury, treatment will be available, including first aid, emergency treatment, and follow-up care as needed. Care for such injuries will be billed in the ordinary manner to the participant or their insurance company.

19.2 Contract Language:

N/A

20.0 Consent Process

20.1 Consent Process (when consent will be obtained):

Subjects who decide to participate based on the phone interview described in section 11 will be mailed a consent form to review. The consent process usually occurs over time through several conversations and discussion of written descriptions of the study between the study coordinator and the potential participant. All applicable potential risks will be discussed with each subject and the subjects will be asked to describe the study in their own words and explain the risks to which they will be exposed to ensure that they have understood the procedures before the consent form can be signed. The IRB-approved consent form will be reviewed and signed on the day of study before any investigation is begun. Written consent will be obtained by the study coordinator or the MR operator, if the study coordinator is not available, in a private room. The forms will be held by the investigators and the subjects will be offered a copy to keep.

20.2 Waiver or Alteration of Consent Process (when consent will not be obtained):

N/A

20.3 Non-English Speaking Participants:

N/A

20.4 Participants Who Are Not Yet Adults (infants, children, teenagers under 18 years of age):

N/A

20.5 Cognitively Impaired Adults, or adults with fluctuating or diminished capacity to consent:

N/A

20.6 Adults Unable to Consent:

- Permission: N/A
- Assent: N/A
- Dissent: N/A

21.0 Setting

21.1 Research Sites:

All procedures will be performed at the CMRR located on the Twin Cities campus at the University of Minnesota.

21.2 International Research:

N/A

22.0 Multi-Site Research

N/A (While the U01 study includes sharing of de-identified data between sites and analysis of multi-site data, each site will obtain their own IRB approvals for MR scanning of subjects with the U01 protocol. Therefore, this study is not classified as multi-site research).

23.0 Resources Available

23.1 Resources Available:

- **Feasibility of recruitment:** The UMN group and the CRC-SCA consortium have extensive experience with recruitment of subjects with ataxias. Even though most of our patient participants are from out of the Twin Cities area, 200 subjects have been successfully enrolled as of the 2017 continuing review of our existing MRS in ataxias protocol (#0502M67488). Under the current protocol, we will continue to collaborate with the CRC-SCA and the NAF headquartered in Minneapolis for recruitment, see section 11.
- **Study Team:** The PI will devote approximately 20% of her time to this project. The local study team includes two study coordinators, two research associates who are responsible of MR data acquisition and analysis and a clinical collaborator who is responsible of the clinical aspects of the project.
- **Training process:** The PI will have an interview with each new study staff member to describe the protocol and research procedures, and clarify the duties of each member. In addition, the protocol will be shared with all study team members.

- **CMRR facilities:** The CMRR is an interdepartmental and interdisciplinary laboratory that provides unique instrumentation, expertise, and infrastructure to enable the faculty, trainees and staff at U Minnesota and other institutions to carry out basic biomedical, translational and clinical research utilizing the capabilities of high magnetic fields. The CMRR is a NIH funded BioTechnology Resource Center (BTRC) through the P41 mechanism and is equipped with an array of high end instruments: Three 3T (Siemens), a 4T (Agilent), two 7T (Siemens) and a recently installed 10.5T system for human studies and a 9.4T (Agilent) and a 16.4T (Agilent) system for animal studies. The 3 Tesla Siemens system will be used for this project.

Clinical: To support translational clinical research CMRR has extensive patient/subject handling facilities with over a 1000 sq. ft of space for Waiting/Reception area and allocated rooms for subject interview and staging rooms adjacent to each magnet suite. There is 3000 sq. ft. dedicated to Clinical Research for human subject preparation and nursing support. This space will be utilized for consenting and administration of the clinical scales and questionnaires.

Computing resources: Each of the MR instruments at the CMRR has a console host workstation along with physiologic monitoring and paradigm presentation computers. The scanners with Siemens consoles (3T, 7T) use Windows based PCs. Each console host is connected by a 10 gigabit per second Ethernet network link for rapid transfer of image data to the data center for post-processing, analysis and storage.

The data center in the CMRR has 59 servers. To handle the amount of image data generated by the MR scanners, twenty four (24) of these servers provide NFS file sharing with a total of 80 Terabytes of RAID data storage. Six (6) of the servers are dedicated to backups for disaster recovery contingency and long term archive and each has an LTO tape auto-loader library attached. Twenty (20) of the CMRR servers are compute nodes, most configured with 8 CPU cores and over 32 gigabytes of RAM memory each.

In addition, as an fBIRN (functional Biomedical Informatics Research Network) grid point-of-presence, the CMRR houses a BIRN node, consisting of a gridftp server, HID (Human Imaging Database), and HID GUI interface server. The BIRN node includes 1TB of RAID storage and four Linux hosts to support distributed high-performance computing and data sharing between institutions at gigabit speeds over a nationwide network of Internet-2 connected computer systems.

Office Space: The PI has an office in the CMRR building. The nursing professional/study coordinator and the research associates also have offices in the CMRR building.

Machine Shops/Electronics Shop: A machine shops and a 1500 sq. ft. full electronics shop is located within the CMRR and is used for

building RF probes, and developing physiological monitoring and recording systems for use in the MR scanner.

